9.2 SAMPLE SIZE DETERMINATION

To assess the primary variable of interest, a power analysis indicated that a total sample of 126 participants would be required to detect medium effects (f = 0.28) with 80% power and $\alpha = 0.05$ using Generalized Linear Model (GLM).

The required sample size to test secondary hypotheses was calculated as 87 and 108 participants for patient reported outcomes and safety, respectively. Therefore, a total sample of 126 participants provides sufficient power for testing secondary hypotheses.

Given an estimated 15% non-compliance rate, the sample size will be increased by 15%, for a total sample size of 147 participants (49 per group).

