2.2 BACKGROUND

The purpose of this double-blind placebo-controlled study is to evaluate the effects of treatment with DSP iontophoresis as an adjunct therapy with PT in pediatric patients with apophysitis of the knee. Patients diagnosed with OSD or SLJ will be randomized to one of three treatment groups: treatment DSP iontophoresis and PT, iontophoresis with placebo and PT, or PT alone. This study will compare the functional and patient reported outcomes of each group.

lontophoresis has been used clinically for over 50 years to deliver drugs transdermally to localized areas of inflammation. Iontophoresis uses a mild electrical current to "push" ionic compounds through the skin and usually increases the rate and extent of absorption compared with passive treatments like the applications of creams, gels or ointments.⁵ The most common drug used clinically for musculoskeletal pain delivered by iontophoresis is DSP. DSP is a phosphate ester prodrug of DSP that transforms the highly lipophilic DSP into a water-soluable molecule suitable for injection. The water solubility and two ionizable groups of DSP make it an ideal candidate for transdermal iontophoresis. Iontophoresis delivers significantly more DSP solution across in vivo human skin compared to passive delivery.⁵

While iontophoresis of DSP is widespread and has been used for decades in musculoskeletal conditions, studies evaluating its benefits in musculoskeletal conditions have been mixed. Some studies have shown improved outcomes in pain and function in a number of musculoskeletal conditions, whereas other studies have shown no benefits.⁵ There have been no studies evaluating its use in the treatment of OSD or SLJ.

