9 STATISTICAL CONSIDERATIONS

9.1 STATISTICAL HYPOTHESES

• Primary Efficacy Endpoint(s):

Length of time to meet RTS criteria as measured in days

Null Hypothesis: Time to achieve RTS criteria for Pediatric patients with apophysitis of the knee who receive iontophoresis with DSP and PT is the same as those who receive iontophoresis with placebo and PT or PT alone.

Alternative Hypothesis: Time to achieve RTS criteria for Pediatric patients with apophysitis of the knee who receive iontophoresis with DSP and PT will be different from those who receive iontophoresis with placebo and PT or PT alone.

• Secondary Endpoint(s):

Efficacy: Patient reported outcomes:

Null Hypothesis: There is not any significant difference in patient reported outcomes (LEFS, FACES pain scale, and Godin Leisure-Time Exercise) between pediatric patients with apophysitis of the knee who receive iontophoresis with DSP and PT and those who receive iontophoresis with placebo and PT or PT alone.

Alternative Hypothesis: Patient reported outcomes (LEFS, FACES pain scale, and Godin Leisure-Time Exercise) of pediatric patients with apophysitis of the knee who receive iontophoresis with DSP and PT will be different from those who receive iontophoresis with placebo and or PT alone.

Safety: Frequency and intensity of adverse events

Null Hypothesis: There is not any significant difference in frequency and intensity of adverse events between pediatric patients with apophysitis of the knee who receive iontophoresis with DSP and PT and those who receive iontophoresis with placebo and PT or PT alone.

Alternative Hypothesis: Frequency and intensity of adverse event among pediatric patients with apophysitis of the knee who receive iontophoresis with DSP and PT will be different from those who receive iontophoresis with placebo and PT or PT alone.

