9.3 POPULATIONS FOR ANALYSES

A Modified Intention-to-Treat Analysis Dataset will be utilized, so that participants who received at least one dose of study intervention will be included in the analysis dataset.

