9.4 STATISTICAL ANALYSES

9.4.1 GENERAL APPROACH

Continuous variables will be expressed as mean, standard deviation, median, and range. Categorical variables will be presented as frequency and percentage. All statistical tests will be two-sided and p < 0.05 will be considered as statistically significant.

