9.4.2 ANALYSIS OF THE PRIMARY EFFICACY ENDPOINT(S)

A GLM will be conducted to test for significant difference in time to RTS (in days) between pediatric patients with apophysitis of the knee who receive iontophoresis with DSP treatment and PT and those

who receive placebo or PT alone. The result will be presented as average time to RTS with 95% confidence interval for intervention groups. Non-informative censoring will be checked to ensure mechanism of censoring is independent of treatment groups.

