9.4.7 INTERIM ANALYSES

While recruitment is ongoing, interim results will be supplied, in strict confidence, to the ISM as frequently as requested. All individuals involved in the interim analyses, including the biostatistician, will be blinded to intervention assignment.

Interim analysis of the study will be conducted based on the alpha spending rule .²⁶ The proportion of the observed sample size (number of patients observed divided by the target sample size) will be considered as the information statistics. The p-value will be adjusted to maintain the overall study power of 0.05, two-sided.

The ISM will inform the PI of the results only if the test statistics exceeds the adjusted p-value in the primary efficacy or safety outcome and if, in the opinion of the ISM, the study should be considered for early termination. The study would not be terminated early if the difference is found only in a secondary outcome of efficacy, the p-value is smaller but close to the adjusted p-value, or when the variance is small. The decision to terminate the study early would be made by the ISM with consultation of a non-treating physician as needed.

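### No contrast is named as deciding the trial, so a significant primary result need not show a drug effect, and power for DSP versus placebo is unstated

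*Combined protocol and SAP*

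**What the plan says.** Section 9.1 states the primary null as time to RTS on DSP+PT, which "is the same as those who receive iontophoresis with placebo and PT or PT alone". Section 9.4.2 repeats this as a single GLM and describes the estimate as follows: "The result will be presented as average time to RTS with 95% confidence interval for intervention groups". No between-arm difference is promised. Section 9.4.1 adds: "All statistical tests will be two-sided and p < 0.05 will be considered as statistically significant". No section ranks the comparisons between arms or divides alpha among them. The only alpha rule, in section 9.4.7, covers interim looks. There the principal investigator hears the result "only if the test statistics exceeds the adjusted p-value in the primary efficacy or safety outcome", but which arms enter that statistic is not said.

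Section 9.2 gives one power statement for the primary endpoint: "a total sample of 126 participants would be required to detect medium effects (f = 0.28) with 80% power" at alpha 0.05, raised to 147 (49 per group) for 15% non-compliance. It gives no SD, no pairwise difference and no power for DSP versus placebo.

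On intent, the primary objective (sections 1.1 and 3) is a three-way comparison. Section 2.2 is narrower: "The purpose of this double-blind placebo-controlled study is to evaluate the effects of treatment with DSP iontophoresis as an adjunct therapy with PT". Section 2.3.3 also asks whether the treatment beats the current home regimen. Sections 4.2 and 6.3 say that the PT-alone arm cannot be blinded, that a high placebo effect is expected in children (no size given), and that the treating therapists make the assessments.

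**The concern.** The two controls answer different questions. DSP versus placebo isolates the drug under blinding. DSP versus PT alone mixes the drug, the patch procedure, expectation, and scoring by a therapist who knows the assignment. With no deciding contrast named, a significant p-value could come from an overall test or from either DSP contrast, and under several of these the PT-alone arm alone can produce it. The trial could then be reported, or considered for early stopping, on a result that says nothing about dexamethasone. The reader also cannot tell what difference between DSP and placebo the trial is sized to find.

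**Working it through.** **Inputs.** From section 9.2: f = 0.28, alpha 0.05, power 80%, N = 126 and 147. From sections 4.1 and 6.3: three equal arms, so n = 42 or 49. Assumed: normal, uncensored days to RTS, common variance on 3n − 3 df, a single look. All patterns of means are assumptions, because the plan gives none.

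**1. The plan's own figure.** Overall F test with 2 and N − 3 df, noncentrality N·f²:
- N = 125: 125 × 0.0784 = 9.80, power 0.797.
- N = 126: 126 × 0.0784 = 9.88, power 0.800.
- N = 147: 147 × 0.0784 = 11.52, power 0.862.

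So 126 is the smallest N for a 2-df overall test. A 1-df contrast at f = 0.28 would need only 103. That the sizing used an overall test is an inference from this match; the plan does not say so.

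**2. What f = 0.28 implies for DSP versus placebo.** If one arm differs by d from two equal arms, f = d·√(2/9), so d = 0.28 / 0.4714 = 0.594. If the arms are equally spaced by e, f = e·√(2/3), so e = 0.28 / 0.8165 = 0.343 and the extremes are 0.686 apart. Pairwise power is from the noncentral t with noncentrality d·√(n/2):

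| Assumed pattern | DSP − placebo (SD) | Power, 42 / 49 per arm |
|---|---|---|
| Placebo midway | 0.343 | 34% / 39% |
| Placebo equals PT alone | 0.594 | 77% / 83% |
| PT alone midway | 0.686 | 88% / 92% |

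The stated 80% does not determine which of these applies.

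**3. No drug effect, PT alone 0.3 SD away.** f = 0.3 × 0.4714 = 0.1414, so f² = 0.02 and the noncentrality is 126 × 0.02 = 2.52 or 147 × 0.02 = 2.94.
- Overall test: rejects 27% / 31%.
- DSP versus PT alone: 28% / 31%.
- Either DSP contrast at 0.05 (simulation): 31% / 34%.
- DSP versus placebo: 5%.

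**4. All arms equal (simulation).** Two unadjusted DSP contrasts give a familywise error of 9%. An overall test, followed by pairwise tests only if it is significant, gives about 4%. The plan states neither procedure.

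**5. Detectable difference at 80% power, 42 / 49 per arm.** DSP versus placebo: 0.616 / 0.570 SD. Overall test with one arm differing: 0.594 / 0.549. The gap is 0.616 − 0.594 = 0.022 and 0.570 − 0.549 = 0.021 SD. With one to three equally spaced interim looks (assumed), O'Brien-Fleming-type spending gives 0.617 to 0.622 / 0.571 to 0.575. Pocock-type spending gives 0.653 to 0.674 / 0.604 to 0.623.

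**6. Cost of testing PT alone second (simulation).** Formal DSP-versus-PT-alone power falls from 88% / 92% to about 34% / 39% if placebo is midway. It falls from 77% / 83% to 65% / 73% if only DSP differs, by 0.594 SD.

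**The case against.** The strongest reply is that the primary objective is itself three-way, so an overall test sized at 126 answers it, and a PT-alone difference is a legitimate answer to a broad question. That stands: the overall test is not an error. It is not, however, evidence about the drug.

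There are real safeguards. The RTS checklist in section 12.3 is itemised, including an 85% hop-distance threshold and a 3-second hold. RTS is rechecked at the Clinic Check visit (section 8.1). Monitors not involved in treatment review every checklist (section 10.1.6). Arm means with intervals would show DSP lying close to placebo. Section 9.4.7 requires the safety monitor's opinion before stopping and rules out stopping on a p-value close to the boundary. These reduce the risk but do not remove it: pain-free status is subjective, the treating therapist scores it, and none of them says which p-value decides.

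A reader might infer a 9% error rate for this trial. That holds only if success means either unadjusted contrast. Pairwise tests made only after a significant overall test would keep a false DSP-versus-placebo claim at or below 5%. A reader might also infer that the controls will be pooled, but sections 1.1 and 4.2 describe them as separate comparators, so that reading is weakly supported. Nor should one assign the whole design effect (0.594 SD) to PT alone and cite the resulting 80% / 86%: that only returns the design power, and no section gives a placebo effect of that size.

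**Conclusion.** The concern holds as a cheap improvement. The plan names no deciding contrast, order or alpha rule across arms, and a significant overall or DSP-versus-PT-alone result would not show a drug effect. The size depends on an unknown PT-alone difference: at an assumed 0.3 SD, 27% to 34% of trials would show significance with no drug effect, depending on the test and arm size. These figures assume normal, uncensored data and a single look, although section 9.4.2 anticipates censoring.

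A reader might go further and conclude that the trial is underpowered for DSP versus placebo. The documents do not support that. At f = 0.28 this power runs from 34% to 92% over the three patterns in which DSP and placebo differ, and no section says which was intended. Confidence is high about the omission. Ranking the placebo contrast first is a design judgement, supported by section 2.2 and by that contrast being the only blinded one.

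**What to change.** - **Sections 9.1 and 9.4.2, with matching wording in 1.1, 3 and 4.1:** keep all three arms. State that a DSP effect is concluded only from DSP+PT versus placebo+PT at two-sided 0.05, reported as a between-arm difference in time to RTS with its 95% CI. Test DSP+PT versus PT alone at 0.05 only if that succeeds; otherwise report the PT-alone difference with its CI as supportive. Label the overall test and placebo versus PT alone as supportive.
- **Section 9.4.7:** apply the efficacy boundary to DSP versus placebo. Because "interim results will be supplied, in strict confidence, to the ISM as frequently as requested", also state the number of looks and the spending function assumed in the power statement.
- **Section 9.2:** keep 147 and restate power for DSP versus placebo: 80% at 0.57 SD with 49 per arm or 0.62 SD with 42 (complete normal data, single look), somewhat larger with alpha spending. Give the assumed SD so that this reads in days. Say which arm size applies, given that under section 9.3 "participants who received at least one dose of study intervention will be included in the analysis dataset".

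**Cost.** No extra patients, provided that a detectable difference about 0.02 SD larger than for the overall test is accepted. Holding 80% power at 0.594 SD instead would need 46 evaluable per arm: 3 × 46 = 138, and 138 / 0.85 = 162.4, so 163 enrolled. The larger cost is the loss of formal power against PT alone shown in step 6, which weakens the section 2.3.3 question. Reporting that difference with its interval in every case keeps the information.

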9.3 POPULATIONS FOR ANALYSES

A Modified Intention-to-Treat Analysis Dataset will be utilized, so that participants who received at least one dose of study intervention will be included in the analysis dataset.

9.4 STATISTICAL ANALYSES

9.4.1 GENERAL APPROACH

Continuous variables will be expressed as mean, standard deviation, median, and range. Categorical variables will be presented as frequency and percentage. All statistical tests will be two-sided and p < 0.05 will be considered as statistically significant.

9.4.2 ANALYSIS OF THE PRIMARY EFFICACY ENDPOINT(S)

A GLM will be conducted to test for significant difference in time to RTS (in days) between pediatric patients with apophysitis of the knee who receive iontophoresis with DSP treatment and PT and those

who receive placebo or PT alone. The result will be presented as average time to RTS with 95% confidence interval for intervention groups. Non-informative censoring will be checked to ensure mechanism of censoring is independent of treatment groups.

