- Duration of exposure: 123 minutes (3 minutes of patch + controller, 120 minutes of patch only)
- Frequency of exposure : maximum twice per week for a total of 12 sessions over a maximum of eight (8) weeks

The I-Bresis[™] System is commercially available and will be used in accordance with approved labeling.

The drug and solution administered via the iontophoresis patch will be DSP and 0.9% sodium chloride (placebo).

Dexamethasone sodium phosphate (DSP) is a synthetic adrenocortical steroid that has potent antiinflammatory effects but lacks the sodium-retaining property of hydrocortisone. Corticosteroids inhibit multiple inflammatory cytokines resulting in decreased edema, fibrin deposition, capillary leakage, and migration of inflammatory cells thereby suppressing inflammation. DSP 0.75 mg has anti-inflammatory activity equivalent to approximately 5 mg of prednisone, 25 mg of cortisone, and 20 mg of hydrocortisone. DSP is long-acting (half-life 200 minutes) and is recommended as adjunctive therapy in a variety of inflammatory disorders and as an immunosuppressant agent.¹¹

0.9% Sodium Chloride injection: is a sterile, nonpyrogenic solution of sodium chloride in water for injection. The solution contains 9 grams/L sodium chloride, USP (NaCl), with 154 mEq/L sodium and 154 mEq/L chloride. The nominal pH of sodium chloride is 5.0 (4.5 to 7.0) and osmolarity is 308 mOsmol/L.²⁴

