6.3 MEASURES TO MINIMIZE BIAS: RANDOMIZATION AND BLINDING

A center-stratified randomization method will be used to maintain balance between treatment groups and centers. Equal number of participants per intervention will be considered to maximize study power. The CHKD Pharmacy Department will hold the randomization key and will prepare bottles of study drug and placebo (see Section 6.2.2 Formulation, Appearance, Packaging, and Labeling).

Treating therapists will assign randomization codes in chronological order as participants enroll in the study. Since the study drug and sodium chloride are identical in appearance, the Treating Therapists will

be blinded to study assignment. Those participants assigned to "Group C", or standard PT alone, will be unblinded to treatment as they will not receive iontophoresis.

In the case of an unexpected and serious adverse event in which knowing the study assignment is critical to the medical care of the participant, the CHKD pharmacist may release this information to the Independent Safety Monitor only, who may share this information with the treating physician.

Both the Treating Therapist and the participants assigned to one of the two iontophoresis groups will be blinded to study treatment. The DSP injection and 0.9% sodium chloride injection are clear, colorless liquids that will be supplied by the CHKD Pharmacy Department in identical looking single-use bottles. Each bottle will contain 1.8 mL of solution and will be labeled in a blinded fashion as either lontophoresis Study Drug "A" or "B".

In this study, the Treating Therapists will also perform all physical therapy assessments. While having a separate group of "assessing therapists" and "treating therapists" minimizes bias even further than the current study design, combining their roles is preferred as it reduces error by minimizing the number of therapists involved, improves completion consistency of the RTS Criteria Checklist, and minimizes scheduling conflicts caused when trying to coordinate two therapist's schedules for every study visit conducted.

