6.4 STUDY INTERVENTION COMPLIANCE

All participants will be asked to attend up to 12 Study Treatment Visits within an 8-week period. Compliance with this request will be documented by the primary Treating Therapist with assistance from front office staff. The Treating Therapist will review all active study participants at his/her site to ensure each participant attended the two scheduled visits. Any study participants who missed a visit will be contacted by the therapist within 24 hours of the missed visit to be counseled on the importance of maintaining the assigned visit schedule and to ascertain if the participant wishes to continue with the study, as described in section 7.3. Lost to Follow-Up.

Participants and/or parents will be asked to verbally confirm or describe compliance with their HEP, patch wear time (for those assigned to Groups A and B), icing recommendations, activity modifications, and bracing and NSAID use as recommended by their referring physician.

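### The primary analysis of days to RTS names no method, date or value for participants who finish or leave without meeting RTS, and its power assumes that everyone has an RTS time.

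*Combined protocol and SAP*

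**What the plan says.** The primary endpoint (Sections 3 and 9.1) is the number of days until the RTS criteria are met. For its analysis, Section 9.4.2 states "A GLM will be conducted to test for significant difference in time to RTS (in days"), followed by "The result will be presented as average time to RTS with 95% confidence interval for intervention groups". Its one sentence on incomplete times is "Non-informative censoring will be checked to ensure mechanism of censoring is independent of treatment groups".

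Other sections determine who can lack an RTS time:

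- **Schedule.** Section 6.1.1 sets "maximum twice per week for a total of 12 sessions over a maximum of eight (8) weeks", and Section 6.4 states "All participants will be asked to attend up to 12 Study Treatment Visits within an 8-week period". Group C follows the same visit numbering and limit (Section 8.1).
- **Observation of RTS.** The checklist is completed at study treatment visits and at the Clinic Check (Section 8.1), and when the intervention is discontinued (Section 7.1).
- **Ending without RTS.** Sections 7.1 and 8.1 let treatment end at 12 applications or 8 weeks. Section 7.3 treats unreachable participants as withdrawn, and Section 7.2 does not replace those already treated.
- **Analysis set.** Section 9.3: "participants who received at least one dose of study intervention will be included in the analysis dataset".

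Section 9.2 derives 126 participants as the number "required to detect medium effects (f = 0.28) with 80% power" under a GLM, then inflates to 147 for 15% non-compliance. Section 9.4.6 reuses the GLM with covariates. Section 9.4.7 measures interim information by participants observed over target. Nothing in Sections 9.3 to 9.4.7 supplies a censoring date, an imputation rule or a censored-data estimator.

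**The concern.** Days to RTS is right-censored: for a participant who stops without RTS, only a lower bound is known. Checking that censoring is unrelated to arm does not analyse that bound, and the plan gives no action if the check fails. Nor is independence of arm the same as non-informative censoring, since loss may track prognosis within every arm.

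Two analysts following Section 9.4.2 could therefore do different things. One might analyse only participants who reached RTS; another might enter the last observed day as the RTS day. They would obtain different estimates, power and possibly error rates for the trial's single primary test, on which early stopping in Section 9.4.7 also relies. Unequal dropout is conceivable: enrolment requires a prescription that includes iontophoresis (Section 5.1), and Group C knowingly receives none (Section 6.3).

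**Working it through.** **1. The plan's own figure.** Inputs from Section 9.2: f = 0.28, α = 0.05, three groups. For a one-way comparison of means, the noncentrality is λ = f²N with 2 and N − 3 degrees of freedom. At N = 126, λ = 0.0784 × 126 = 9.88 and power is 80.0% (79.7% at N = 125; 86.2% at N = 147). The figure reproduces exactly when every analysed participant has an observed time. The inflation, 126 × 1.15 = 144.9, rounds up to 49 per group and is for non-compliance.

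**2. When observation can end.** Twelve visits at two a week leave 11 gaps of 3.5 days, so the last falls at day 38.5. A Clinic Check soon after falls near day 42. Spread over the full window, visits end at day 56.

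**3. Illustration of the two informal rules.** The documents give no RTS rate, hazard ratio or dropout rate. Assumed: 49 per arm, Weibull times (shape 1.5), hazard ratio 1.8 for DSP against both controls, control RTS of 60, 75 or 90% by day 56, dropout uniform over 56 days, 4,000 trials per cell. Power with 15% dropout in every arm and a Clinic Check:

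| Visits | Control RTS | Achievers only | Last day as RTS day | Log-rank |
|---|---|---|---|---|
| Twice weekly | 60% | 6.2% | 35.8% | 56.7% |
| Twice weekly | 75% | 12.1% | 49.4% | 69.0% |
| Twice weekly | 90% | 28.4% | 64.4% | 78.4% |
| Spread to day 56 | 60% | 14.5% | 48.8% | 69.9% |
| Spread to day 56 | 75% | 24.8% | 58.9% | 76.3% |
| Spread to day 56 | 90% | 52.4% | 70.8% | 81.8% |

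On the twice-weekly schedule the true difference in mean time restricted to day 42 is 4.5–6.2 days. Achievers-only gives 1.4–3.3 and last-day 4.1–5.7.

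**4. No dropout, twice weekly.** Last-day scoring is unbiased for the restricted mean difference (4.5–6.1 days), with power 48–71% against 60–81% for log-rank.

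**5. Unequal dropout.**

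- No true effect, 30% dropout in one arm and 10% in the others: last-day false positives are 17.5, 12.5 and 9.2% (twice weekly) and 18.7, 14.9 and 11.1% (spread) as control RTS rises; log-rank stays at 4.9–5.8%. With 20% against 10%, last-day gives 5–8%.
- Hazard ratio 1.8, 30% dropout in DSP and 10% elsewhere: last-day inflates the difference, to 6.3–6.9 against 4.5–6.1 days (twice weekly) and 8.9–10.4 against 7.3–8.1 (spread).
- Reversed, 10% in DSP and 30% elsewhere: it shrinks to 1.8–4.1 and 3.2–5.1 days.

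**6. Benign case.** With control RTS of 97–99% and 5% dropout, last-day power is 76–79% against 83% for log-rank.

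**7. Dependence on proportional hazards.** Replacing the Weibull by a lognormal shift (σ 0.6, DSP times divided by 1.39, control RTS 75–97%) with no dropout gives about 73–78% for last-day and 71–76% for log-rank.

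**8. Power on the log-rank scale.** For 80% power at two degrees of freedom, 9.63 = D × (2/9) × (ln HR)², where D is the number of RTS events and 2/9 = (1/3)(2/3) sets DSP against two equal controls. If 60, 75 or 90% of 147 reach RTS under observation, D = 88, 110 or 132. For D = 88, (ln HR)² = 9.63/19.56 = 0.492, so HR = 2.02. The others give 1.87 and 1.77.

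**The case against.** The strongest reply is that a GLM need not be a means model. A Poisson model with a follow-up offset, or a binomial model with complementary log-log link for times grouped by visit, handles censoring and would fit the words of Section 9.4.2, which plainly anticipates censoring. That stands as far as it goes: a reader might infer that any GLM is invalid here, and that would be too strong. The fault is that no such form is specified, while the effect size and the average-time summary both point to a comparison of means.

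A reader might also infer that the plan carries a 9–19% false-positive rate. The documents do not support this. Those figures need last-day scoring, which no section proposes, and 30% against 10% dropout, which no section predicts. The 15% in Section 9.2 is non-compliance. The planned censoring check might catch so large an imbalance: a simple chi-square check, itself an assumption, would flag 30/10/10 in about 76% of trials but 20/10/10 in only 30%. No consequence is stated, so this mitigates only in part. Without dropout, type I error stays near 5%.

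Nor is log-rank always more powerful. Its advantage in the table comes from simulated proportional hazards and from dropout; under a lognormal shift without dropout, last-day scoring is equal or slightly better.

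Section 4.1 dates all follow-up from meeting RTS and may presume that nearly everyone does. No RTS rate supports that, and Section 8.1 provides for eight weeks without it. Finally, Section 6.1.1 defines the intervention as DSP by iontophoresis, so it is unclear how the at-least-one-dose rule covers PT-alone participants. That does not supply the missing rule.

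**Conclusion.** The concern holds as an underspecified primary analysis whose sample size presumes complete RTS times. The omission and the exact reproduction of N = 126 rest on the documents alone. The consequences are conditional. In a means model, dropping participants without RTS shrinks the difference and loses power. Last-day scoring is unbiased for the restricted mean without dropout, but can inflate, shrink or create a difference when dropout differs by arm. The sizes shown rest on assumed hazard ratio, time distribution, RTS rates and dropout, so they give direction and range and do not forecast this trial. If nearly all participants reach RTS under observation with little dropout, the loss from last-day scoring is about 4–7 points of power. The matter still needs settling before analysis, because the primary result should not turn on an unplanned choice.

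**What to change.** **Section 9.4.2.** Pre-specify one censoring-valid primary analysis. One option is a three-group log-rank test stratified by centre, with a Cox model; centre is the randomisation factor (Section 6.3: "A center-stratified randomization method will be used to maintain balance between treatment groups and centers"). The other, if the average is the target or proportional hazards is doubtful, is a comparison of restricted mean time to RTS. In either case:

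- report restricted mean time per arm with 95% CI and Kaplan-Meier curves, which keeps the intended summary;
- censor participants without RTS at their last RTS check, including the Clinic Check;
- fix the horizon at a day the schedule supports, since checks may end near day 42;
- state whether the event date is the first visit at which RTS is met or the one confirmed at the Clinic Check;
- add a sensitivity analysis for informative dropout, scoring lost participants as meeting RTS at the next scheduled check, then as not meeting it to the horizon, varied by arm.

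**Sections 9.4.6 and 9.4.7.** Use the same censoring-valid model with covariates. If log-rank is chosen, base interim information on RTS events.

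**Section 9.2.** Restate power for the same 147 participants as a detectable hazard ratio: about 2.02, 1.87 or 1.77 (unstratified) if 60, 75 or 90% reach RTS under observation, and slightly larger when stratified by centre.

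**Section 8.1.** The Clinic Check is tied to RTS clearance or eight weeks of treatment, yet treatment can also end at 12 visits before week 8. These statements must be reconciled, because they determine the last RTS check.

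**Cost.** Rewording of these sections and standard software; no new visits or data. The stated 80% power no longer follows. In the 15%-dropout scenarios, with or without a Clinic Check, power is 54–82% for log-rank, 52–78% when stratified by six centres (a cost of 2–5 points) and 44–81% for the restricted mean. Log-rank and Cox lose power under non-proportional hazards and are biased by informative dropout. If 20% of the DSP arm stop attending once RTS-ready, on top of 10% random dropout in every arm, log-rank false positives reach 9–14% and power falls from 58–83% to 25–40%. That is the reason for the sensitivity analysis.
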